6.3.2. Exclusion criteria

- E-1. Concomitant hepatic insufficiency, deep venous thrombus in target limb, uncorrected coagulation disorders, or current immunodeficiency disorder
- E-2. Life expectancy less than 12 months
- E-3. Patient currently taking coumarin/warfarin which, in the opinion of the attending physician, interferes with the patient's treatment
- E-4. Any significant medical condition which, in the attending physician's opinion, may interfere with the patient's optimal treatment
- E-5. Patient currently participating in another investigational drug or device study that has not completed the primary endpoint or that clinically interferes with the endpoints of this treatment
- E-6. Patient unable to give consent
- E-7. Pregnant or breastfeeding women
- E-8. Documented myocardial infarction or stroke within previous 90 days
- E-9. Patients suffering from renal insufficiency (GFR value less than 30 ml/min/1.73 m²) who are not on haemodialysis
- E-10. Patients with vasculitis and/or untreated popliteal aneurysms
- E-11. Patients with acute limb ischaemia
- E-12. Prior peripheral arterial bypass procedure above or below the knee which could inhibit proximal inflow to the stent graft
- E-13. Lower extremity venous disease with significant oedema in the target limb that may inhibit the procedure and/or jeopardize wound healing, in the investigator's opinion
- E-14. Known or suspected systemic or severe infection (e.g., WIfI foot Infection grade of 3)
- E-15. Known or suspected allergies or contraindications to stainless steel, nickel, or contrast agent that cannot be adequately pre-treated, or patients who cannot receive anticoagulation or antiplatelet aggregation therapy
- E-16. Severe heart failure, which in the opinion of the investigator may compromise subject's ability to safely undergo a percutaneous procedure (e.g., known ejection fraction of < 40%, NYHA Classification III-IV)

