7.1. Statistical design, method and analytical procedures

Subject demographics, baseline characteristics and medical history will be summarized descriptively. Mean and standard deviation will generally be reported for continuous variables; median and range may be reported instead if the data distribution is skewed. Frequencies and proportions will be reported for categorical variables.

The design of this post-market study (PMS) is mirroring that of the early feasibility study (EFS) conducted in the United States of America, allowing for both datasets to be pooled in order to perform a statistical analysis on a larger cohort of patients.

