7.2. Sample size

In the absence of formal statistical hypotheses for this single-arm, post-market study, the planned sample size could not be derived statistically. It was however estimated that a cohort of approximately twenty (20) subjects would provide sufficient data in order to meet the objectives defined in the study.

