7.4. Specification of subgroups for analysis

If relevant, subgroup analyses may be performed based on baseline or treatment parameters—Student's (or Wilcoxon's according to the normality of the distribution) and Chi-2 (or Fisher's) between-group tests will then be used for quantitative and qualitative parameters, respectively.

In particular, renal function characteristics at baseline (GFR value and/or dialysis status) may be used to define subgroups for the purpose of the analysis. Specifically, patients on dialysis are excluded from the early feasibility study (EFS), which will be taken into consideration when pooling datasets from both cohorts. Safety and effectiveness results from dialysis and non-dialysis patients will be compared.

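### Does section 7.4 need to name the dataset for the dialysis comparison and a method for handling the feasibility study's dialysis exclusion?

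*Combined protocol and SAP*

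**What the plan says.** The second paragraph of section 7.4 takes three steps. It allows renal subgroups: "renal function characteristics at baseline (GFR value and/or dialysis status) may be used to define subgroups for the purpose of the analysis". It notes a difference from the US study: "patients on dialysis are excluded from the early feasibility study (EFS), which will be taken into consideration when pooling datasets from both cohorts". It then commits to one comparison: "Safety and effectiveness results from dialysis and non-dialysis patients will be compared". The paragraph before it is permissive ("If relevant, subgroup analyses may be performed based on baseline or treatment parameters") and adds that, where subgroups are analysed, Student/Wilcoxon and Chi-2/Fisher "between-group tests will then be used for quantitative and qualitative parameters, respectively".

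Three other places bear on this. Section 7.1 says that the two designs mirror each other, "allowing for both datasets to be pooled in order to perform a statistical analysis on a larger cohort of patients". Exclusion E-9 in section 6.3.2 removes "Patients suffering from renal insufficiency (GFR value less than 30 ml/min/1.73 m²) who are not on haemodialysis", so patients on haemodialysis can enter this study. Section 7.2 states that there are no formal hypotheses and judges that "a cohort of approximately twenty (20) subjects would provide sufficient data in order to meet the objectives defined in the study".

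**The concern.** Read quickly, section 7.4 seems to leave the dialysis comparison open in three ways.

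- Its status: dialysis *may* define a subgroup, yet the results *will* be compared.
- Its dataset: the commitment directly follows the sentence on pooling, so a within-study and a pooled reading both fit.
- Its method: the plan says that the EFS exclusion will be allowed for, but not how.

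The second and third matter together. The EFS supplies no dialysis patients, so in a pooled set the dialysis group is drawn entirely from this study and the non-dialysis group from both. If outcomes differ between the studies for any reason, such as selection, operators or wound care, a crude pooled contrast credits part of that difference to dialysis. Two analysts could follow the section and report different dialysis results.

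**Working it through.** The plan gives no alpha, power, effect size, dialysis share or EFS size, so there is no stated figure to reproduce. The check is a reading of the text, followed by a bound on what the gap could cost.

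**1. May and will.** The wording runs from general to specific: subgroups in general are optional, renal characteristics are one option, and dialysis against non-dialysis is the one comparison promised. The last sentence carries no condition, so an analyst who leaves the comparison out has not followed the plan. There is no contradiction.

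**2. Which analyses fit the text.** There are three candidates.

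- *Within this study.* The EFS plays no part.
- *Pooled, stratified by study.* In a Mantel-Haenszel risk difference a stratum has weight n1 × n0 / N. In the EFS n1 (on dialysis) is 0, so its weight is 0 and the estimate is the within-study one. A linear model of risk with one term for study and one for dialysis has three occupied cells and three parameters, so its dialysis coefficient is again the within-study difference.
- *Pooled, crude.* This is the only candidate that gives a different answer. It is also the one that ignores the exclusion which section 7.4 undertakes to consider.

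**3. Size of the shift if the crude pooled contrast were used.** Let n_d be the number on dialysis in this study and n_E the EFS size, with no true dialysis effect.

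Shift = w × (rate in this study − rate in the EFS), where w = n_E / (n_E + 20 − n_d).

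The 20 comes from sections 6.1.1 and 7.2. *Assumed, not in the documents:* n_E from 10 to 30 and n_d from 4 to 8.

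- Smallest w: 10 / (10 + 16) = 10/26 = 0.385.
- Largest w: 30 / (30 + 12) = 30/42 = 0.714.

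| Gap between studies (assumed) | Shift in the crude difference |
|---|---|
| 0 points | 0 |
| 10 points | 3.8 to 7.1 points |
| 20 points | 7.7 to 14.3 points |

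**4. Shift against noise.** Take event-free rates of 55% here and 75% in the EFS (assumed). The Wald 95% half-width is 1.96 × √[0.55 × 0.45 / n_d + r(1 − r) / n_0], where n_0 and r are the size and average rate of the non-dialysis group.

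- n_d = 4, n_E = 10: n_0 = 26, r = (16 × 0.55 + 10 × 0.75)/26 = 0.627. Half-width 52.2 points, shift 7.7.
- n_d = 8, n_E = 30: n_0 = 42, r = (12 × 0.55 + 30 × 0.75)/42 = 0.693. Half-width 37.2 points, shift 14.3.

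Within this study alone the half-width is 54.5 points for n_d = 4 and 44.5 for n_d = 8. Pooling therefore gains little, and an analyst has little reason to prefer the crude version.

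**5. False positives on the crude pooled reading.** These are exact rejection rates for Fisher's test at an assumed two-sided 0.05, with no dialysis effect, over all 105 combinations of n_d and n_E.

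| Rate here / in the EFS (assumed) | Rejection rate |
|---|---|
| 65% / 65% | 1.6% to 3.5% |
| 55% / 75% | 3.4% to 11.5% |
| 75% / 55% | 0.4% to 7.3% |

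With no gap the rate stays below 5% throughout. The 11.5% is the worst cell under an assumed 20-point gap.

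**6. What the within-study comparison can show.** With 20 patients and the same assumed 0.05 level, a single dialysis patient can never give p < 0.05, because the smallest possible p is 1/20. With 4 on dialysis the observed difference must be at least 50.0 points (2/4 against 0/16). The smallest significant difference at any split is 37.5 points (3/8 against 0/12, p = 56/1140 = 0.049). This is a limit of sample size that no wording in section 7.4 would remove. For safety the denominator may exceed 20, since sections 2.7 and 6.3.3 exclude roll-in subjects only from the endpoint analysis and section 6.1.1 allows up to 25 patients.

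**The case for a change.** The best case for a change is that this is the only subgroup comparison the plan firmly promises, that it covers both safety and effectiveness, and that no other section names its dataset. Section 7.1 says only that pooling is possible, and section 7.5 deals with missing data and patient accountability. The structural point needs no outside figure: it follows from E-9 and from the EFS exclusion stated in section 7.4. One or two sentences would settle it and no data collection would change.

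The facts in that case stand; the inference that the plan must change does not. A method left unstated is not a wrong method, and the sponsor has already identified the one feature that could mislead. The documents show neither that a crude pooled contrast is intended nor that the two studies differ.

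Stronger rewrites carry costs of their own. Replacing the between-group test with separate intervals would contradict the first paragraph of section 7.4 unless that were edited too. It would also leave quantitative outcomes such as pain and EQ-5D without a stated comparison. Restricting every pooled estimate to non-dialysis patients, or stratifying every one by study, would alter the larger-cohort analysis that section 7.1 allows for.

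**Conclusion.** No change is needed. Section 7.4 omits a detail that a competent analyst fills in the obvious way: compare dialysis with non-dialysis patients within this study, or stratify by study, which gives the same contrast. The movement from *may* to *will* is ordinary drafting.

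The comparison is exploratory, in a study without formal hypotheses, and this study's own estimate of amputation-free survival does not depend on it. Even on the least careful reading, the distortion is zero if the studies agree. With an assumed 20-point gap it is 7.7 to 14.3 points, inside a 95% half-width of about 37 to 52 points. These sizes rest on assumed values for EFS size (10 to 30), dialysis patients here (4 to 8 of 20) and event-free rates. The conclusion does not depend on them. It rests on the plan's own undertaking to allow for the exclusion and on the absence of any instruction to pool without doing so.

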7.5. Treatment of missing, unused, or spurious data

The number of missing data will be presented for each variable as part of the descriptive statistical analysis. Subjects withdrawn and/or lost to follow-up will be presented in a patient tree showing detailed patient accountability at each follow-up visit.

8. Data management

Electronic Case Report Forms (eCRFs) will be specifically developed on the [IBM Clinical Development](#) platform for the study. The eCRFs will be used for data collection during the course of the study and must be completed for all patients enrolled into the study. It is the responsibility of the investigator to ensure the quality of the data collected and recorded in the eCRFs. The eCRFs will be reviewed for errors, omissions, internal consistency, and to ensure that the investigator has signed and dated the appropriate sections; entered data will be audited for verification and validation purposes.

Data collection will include clinical data, as well as medical images based on the clinical endpoints outlined above. Images will be centrally analysed by the independent committee. Specifically, the role of the core laboratory will be (1) to assess the anatomical eligibility of all candidates at baseline and (2) to assess the safety endpoint at follow-up timepoints.

The eCRFs are compliant with FDA 21 CFR Part 11 requirements. All information and data concerning patients or their participation in this study will be considered confidential. Only authorized personnel will have access to this confidential information. All data used in the analysis and reporting of this evaluation will be without identifiable reference to individual patients. Patients will be identified using a six-character sequence (ISO 3166-1 α-2 country code; two-letter site code; two-digit patient number).

The investigator must retain paper copies of study records. LimFlow SA will maintain copies of correspondence, data, and other records related to the study. LimFlow SA will maintain records related to the signed Investigator's Agreements.

LimFlow SA will provide devices only to participating investigators, obtain a signed Investigator's Agreement, and provide the investigator with the information necessary to conduct the study. The training of appropriate clinical site personnel will be the joint responsibility of the Sponsor and the Monitor. To insure uniform data collection and Clinical Investigation Plan compliance, the Sponsor and/or the Monitor will present a formal educational session to study site personnel which will review the Clinical Investigational Plan, techniques for the identification of eligible patients, instructions on in hospital data collection, methods for soliciting data from alternative sources, schedules for follow-up with the study site coordinators, and regulatory requirements.

9. Amendments to the clinical investigation plan

The investigator will not implement any changes without the prior agreement of LimFlow SA and review by the Ethics Committee with documented approval/favourable opinion, except when the change involves logistical or administrative aspects of the investigational site.

10. Deviations from clinical investigation plan

The investigator is not allowed to deviate from the clinical investigation plan, except under emergency circumstances to protect the rights, safety and well-being of a study subject. Such deviations shall be documented and reported to LimFlow SA and the Ethics Committee as soon as possible depending on local regulatory requirements.

11. Device accountability

Each component of the LimFlow System will be traceable via lot and serial number. Records of device shipments will be maintained at the LimFlow facility in accordance with LimFlow's quality system and internal procedures. Product Details will be captured on the case report forms for each subject receiving treatment with the LimFlow System to provide traceability.

LimFlow SA will supply the device; any requests for additional materials, equipment, service, or information shall be directed to LimFlow SA. An inventory of materials will be taken at monitor site visits.

12. Statements of compliance

This post-market study shall be conducted in accordance with the ethical principles that have their origin in the Declaration of Helsinki ("Ethical Principles for Medical Research Involving Human Subjects", 18th World Medical Association General Assembly, Helsinki, Finland, June 1964) and in compliance with the standard ISO 14155:2020 ("Clinical investigation of medical devices for human subjects—Good clinical practice") as well as any regional or national regulations, as appropriate.

This post-market study shall not begin until the required approval/favourable opinion from the Ethics Committee or regulatory authority have been obtained, if appropriate. Any additional requirements imposed by the Ethics Committee or regulatory authority shall be followed, if appropriate

LimFlow SA subscribed to an insurance that shall be provided for all study subjects, in accordance with regional or national regulations, as appropriate.

13. Informed consent process

The sponsor will provide centres with a sample informed consent document that the centre may modify to meet individual Ethics Committee requirements. Any modifications of the informed consent document must be submitted to LimFlow SA for approval prior to submission to the Ethics Committee.

An informed consent form must be signed by each patient prior to study enrolment and implant of the study device. Informed consent will be obtained according to the Declaration of Helsinki ("Ethical Principles for Medical Research Involving Human Subjects", 18th World Medical Association General Assembly, Helsinki, Finland, June 1964), requirements of the standard ISO 14155:2020 ("Clinical investigation of medical devices for human subjects—Good clinical practice"), and individual institution guidelines. Patient informed consents will be audited to ensure they have been signed prior to the treatment procedure and that the correct version was used.

The subject screening and recruitment process will be performed by the site medical personnel and should follow the steps below:

1. Critical limb ischaemia patients with no endovascular or surgical treatment options are initially identified by the site investigators
2. No-option patients meeting the LimFlow System indications and contraindications (as provided in the instructions for use since the LimFlow System is commercially available) can be scheduled for a percutaneous deep vein arterialization
3. Patients scheduled for a LimFlow intervention are asked whether they would be willing to participate to the study (inclusion/exclusion criteria are aligned with the CE-marked indications/contraindications)
4. Patients candidate to the study are subsequently enrolled, treated, and followed as per standard of care (the study protocol does not require more visits than what is considered standard of care)

14. Adverse events, adverse device effects and device deficiencies

14.1. Definitions

The ISO 14155:2020 “*Clinical investigation of medical devices for human subjects—Good clinical practice*” definitions will be used for this post-market study and are provided in Table 6 below.

Table 6. Definitions of adverse events and adverse device effects

Adverse event (AE)	Adverse device effect (ADE)
Any untoward medical occurrence, unintended disease or injury, or untoward clinical signs (including abnormal laboratory findings) in subjects, users or other persons, whether or not related to the investigational medical device	Adverse event related to the use of an investigational medical device or procedure
Serious adverse event (SAE)	Serious adverse device effect (SADE)
Adverse event that 
▪ led to death,▪ led to serious deterioration in the health of the subject, that either resulted in
▪ a life-threatening illness or injury, or▪ a permanent impairment of a body structure or a body function, or▪ in-patient or prolonged hospitalisation, or▪ medical or surgical intervention to prevent life-threatening illness or injury or permanent impairment to a body structure or a body function▪ led to foetal distress, foetal death or a congenital abnormality or birth defect	Adverse device effect that has resulted in any of the consequences characteristic of a serious adverse event 
▪ Anticipated serious adverse effect (ASADE): SADE which by its nature, incidence, severity or outcome has been identified in the risk analysis report▪ Unanticipated serious adverse effect (USADE): SADE which by its nature, incidence, severity or outcome has not been identified in the risk analysis report

Note: a planned hospitalisation or intervention for a pre-existing condition without deterioration in health is not considered to be an adverse event.

Device deficiency is defined as inadequacy of a medical device with respect to its identity, quality, durability, reliability, safety or performance, including malfunctions, use errors, and inadequate labelling.

14.2. Reporting

All adverse events will be documented in the case report forms, including date of onset, symptoms, treatment, duration (or the fact that it is still continuing), resolution, and assessment of both the seriousness and the relationship to the device. Similarly, all device deficiencies will be documented in the case report forms. In addition, all serious adverse events and serious adverse device effects must be reported immediately after discovery by any site member to LimFlow SA.

LimFlow SA will report such an event and the results of an investigation to the appropriate regulatory authorities in compliance with applicable regulatory requirements. If LimFlow SA and the investigator determine that the events present an unreasonable risk to the subjects, LimFlow SA will terminate all or parts of the study.

The reporting of any serious adverse events and/or serious adverse device effects to the Ethics Committee is the sole responsibility of the site's Principal Investigator.

All adverse events will be adjudicated by the independent committee in order to assess the procedure or device relatedness as well as the event seriousness.

14.3. Foreseeable events

The following adverse events may occur when performing percutaneous deep venous arterialization and will be specifically assessed during the course of the study:

- Allergic reaction, including anaphylactic shock and Quincke's oedema

- Vascular complications at access site, including bleeding events and hematoma
- Arterial and venous thromboembolic events, including angina or myocardial infarction, stroke or transient ischaemic event, pulmonary embolism, deep vein thrombosis, and limb ischaemia
- Contrast-induced nephropathy and renal failure
- Oedema
- Local or systemic infection
- Pain

14.4. Management

If the investigator determines that an adverse event occurs the investigator will manage the subject as he/she would if a similar event occurred during a standard interventional procedure. The investigator will formulate an appropriate management plan for the subject using only conventional, non-investigational methods. Medical management of the subject is the responsibility of the investigator and/or other trained, licensed medical personnel. It is at the discretion of the investigator as to whether the percutaneous deep vein arterialization procedure should be continued.

All subjects with adverse events will be followed with the appropriate treatment and medical supervision until either the end of the study (*i.e.*, 12 months) or resolution of the adverse event (whenever possible), whichever is the longer follow-up.

14.5. Emergency contact details

Serious adverse events and serious adverse device effects must be reported to the sponsor LimFlow SA. Contact details are as follows:

LimFlow SA
 [name]
Director of European Clinical Affairs
 E-mail: [contact]
 [contact]

15. Vulnerable population

Not applicable for this post-market study.

16. Suspension or premature termination of the investigation

In the event of unforeseen or increased risks to subjects encountered during the course of the study, LimFlow SA, the Ethics Committee, the Competent Authority, or the Investigator may decide to suspend or terminate the clinical study. Such decision would be made after discussion with all parties.

If the investigator terminates or suspends the study without prior agreement with LimFlow SA, he/she will promptly provide all details to the institution, LimFlow SA, and the Ethics Committee. If the investigation is terminated or suspended by LimFlow SA, the investigator will be promptly informed, who must then inform the Ethics Committee. If the Ethics Committee terminates or suspends the study, the investigator will promptly inform LimFlow SA with written explanation.

Subjects will continue to be followed per the clinical investigational protocol unless it has been determined by the investigator that the continued follow-up may jeopardize the rights, safety, and/or welfare of the subject.

17. Publication policy

The data generated by this clinical study are the property of the sponsor, and should not be disclosed without their prior written permission. These data may be used by the sponsor now and in the future for presentation or publication at sponsor's discretion or for submission to governmental regulatory agencies. The principal investigator may publish or present the study results with prior consent of the sponsor, but will not disclose confidential information. Prior to submission by a principal investigator for publication or presentation, the sponsor will be provided with the opportunity to review the submission for confidential information and accuracy. The possibility of a publication in a peer-reviewed journal will be sought.

18. Definitions

Amputation	Major amputation is defined as amputation of the index limb at the level above the ankle. Minor amputation is defined as amputation(s) of the index limb (including metatarsals) at the level below the ankle.
Amputation-free survival	Defined as the percentage of subjects with limb salvage and survival.
Arteriovenous fistula	An unplanned, anatomical connection between the access artery and the adjacent vein that is demonstrated by arteriography or ultrasound, most often characterized by a continuous bruit.
Clinically-driven major re-intervention	Creation of a new surgical bypass, the use of thrombectomy or thrombolysis (i.e. , procedures done in the setting of lost primary-assisted patency), or major surgical revision such as a jump graft or an interposition graft performed for occlusion of the stent graft.
Deterioration in renal function	Defined as a $\geq 25\%$ increase in serum creatinine after using iodine contrast agents, without another clear cause for kidney injury.
Embolism	The sudden blocking of an artery by a clot or other material that has been brought to its site of lodgment by the blood current (embolus). Potential sources of emboli include blood clots, fat globules, air bubbles, tissue, clumps of bacteria, thrombus or foreign material.
Limb salvage	Freedom from major amputation.
Myocardial Infarction (MI)	The term myocardial infarction should be used when there is evidence of myocardial necrosis in a clinical setting consistent with myocardial ischaemia. Specifically, the criteria provided by the universal definition of myocardial infarction will be used for diagnostic purposes.
Occlusion	Absence of flow on colour Doppler ultrasound and/or absence of flow on angiographic images (conventional or CT-scan).
Patency	Primary patency is defined as the absence of occlusion of the stent graft without prior clinically-driven major re-intervention of the stent graft. Secondary patency is defined as the absence of occlusion of the stent graft with or without prior clinically-driven major re-intervention of the stent graft.
Pseudoaneurysm	A blood vessel abnormality resembling an aneurysm (localized abnormal dilatation of a blood vessel) but consisting of a collection of blood with persistent flow outside an artery, contained by surrounding tissue and due to a leaking hole through all layers of the arterial wall. The leaking hole is due to injury of (e.g. , rupture of or trauma to) the arterial wall. The pseudoaneurysm is usually identified by angiography or ultrasound.
Retroperitoneal bleeding	Bleeding from an injured vessel, with deposition of blood into the retroperitoneal space (between the peritoneum and the posterior abdominal wall).
Stroke	A stroke is any sudden development of neurological deficits, such as vertigo, numbness, aphasia, or dysarthria due to vascular lesions of the brain such as haemorrhage, embolism, thrombosis, or rupturing aneurysm.
Success	Technical success is defined as completion of the endovascular procedure and immediate morphological success with successful placement of the arterial and venous catheters in the desired location in the limb, and ability to place the stent graft. Procedural success is defined as combination of technical success, and absence of all-cause death, above-ankle amputation or clinically driven major re-intervention of the stent graft.
Survival	Freedom from all-cause mortality.
Thrombosis	Formation or development of a blood clot or thrombus, specifically in the arterial or venous system of the ipsilateral distal extremity.
Transient Ischaemic Attack (TIA)	Focal neurologic abnormalities of sudden onset and brief duration that reflect dysfunction in the distribution of the affected artery. Transient ischaemic attack is characterized by fully reversible symptoms of short duration.

19. Bibliography

